A Phase 2 multi-center, randomized, double blind, placebo-controlled, parallel group study to evaluate the efficacy and safety of T-817MA in patients with mild to moderate Alzheimer's Disease (US202)

Protocol & SAP Synopsis

2018.7.12

NCT02079909

PROTOCOL TITLE	A Phase 2 multi-center, randomized, double blind, placebo-controlled, parallel group study to evaluate the efficacy and safety of T-817MA in patients with mild to moderate Alzheimer's Disease (US202)
STUDY SPONSOR	Toyama Chemical Co., Ltd.
COORDINATING CENTER	Alzheimer's Disease Cooperative Study (ADCS)
STUDY PHASE	2
INDICATION	For the treatment of mild to moderate Alzheimer's disease.
OBJECTIVES	
The primary objective is to evaluate the efficacy of T-817MA as measured by ADAS-cog and ADCS-CGIC.
 
The secondary objectives are:
 
 • To evaluate the safety and tolerability of T-817MA measured by clinical safety laboratories, physical examinations, ECGs and solicitation of adverse events. • To evaluate the efficacy of T-817MA as measured by ADCS-ADL, FAQ, Neuropsychiatric Inventory (NPI) and Mini-mental State Examination (MMSE).
ADDITIONAL OBJECTIVES	Population pharmacokinetics of T-817 will be analyzed. Volumetric MRI (vMRI) scans will be evaluated. CSF biomarkers will be evaluated in a subset of the study population.
PRIMARY ENDPOINTS	The change in the ADAS-cog and ADCS-CGIC from Baseline to Week 52 between each T-817MA treatment group (high or low dose) and the placebo group.
SECONDARY ENDPOINTS	
 • The change in the ADAS-cog from Baseline to Weeks 12, 24, 36, 44 and 56. • The change in the ADCS-CGIC from Baseline to Weeks 12, 24, 36 and 44. • The change in the MMSE from Baseline to Weeks 12, 24,

	
36, 44, 52 and 56.
 
 • The change in the ADCS-ADL, FAQ and NPI from Baseline to Weeks 12, 24, 36 and 52. • Safety as measured by occurrence of adverse events, clinical laboratory tests, vital signs, physical examinations, ECGs, use of concomitant medications, and the C-SSRS Pediatric.

STUDY DESIGN
	
This is a Phase 2 multi-center, randomized, double blind, placebo-controlled, parallel group study.
 
Patients will be screened at the investigative site in order to determine their eligibility for the study. A central review of screening results will then be conducted and, if appropriate, permission will be granted to randomize the patient.
 
At Baseline, patients will be randomized to one of three treatment groups: placebo, 224 mg T-817MA, or 448 mg T-817MA in a 1:1:1 allocation. Donepezil or rivastigmine transdermal system, concomitant treatment for Alzheimer’s disease, will be required to be taken as prescribed by the PI or other prescribing physician, and will be encouraged to be maintained throughout the study. Memantine will be allowed only when prescribed in combination with donepezil or rivastigmine transdermal system.
 
Patients will be seen every four weeks for the first 12 weeks of the study, and then will be seen every 6 weeks thereafter until Week 36, then at Week 44 and Week 52. A final follow-up visit will be conducted at Week 56.
 
Safety evaluations will be carried out at each visit. Efficacy will be assessed every 12 weeks beginning at Baseline through Week 36 then at Week 44 and 52 and finally during the follow up visit at Week 56. Volumetric MRI scans of the brain will be done at Screening and Week 52. Blood collection for population pharmacokinetic (PPK) assessments will be done at Baseline and Weeks 12, 24, 36, 44 and 52. A subset of patients will undergo lumbar puncture at Weeks 0 and 52 to evaluate

	CSF biomarkers.
SAMPLE SIZE	In order to arrive at 110 evaluable patients in each study group, it is necessary to randomize at least 450 patients (at least 150 per group), assuming a 26% dropout rate during the treatment period.
KEY ELIGIBILITY CRITERIA	
 • Ages 55 to 85 years (inclusive), with probable AD • MMSE 12-22 (inclusive) at screening • Receiving donepezil or rivastigmine transdermal system treatment for at least 4 months prior to Baseline and on a stable dose for 3 months prior to Baseline • Brain MRI or CT consistent with Alzheimer’s disease • Residing in the community with a designated study partner who will accompany the patient to all clinic visits and participate in the evaluations (see protocol details) • Informed consent or Legally Authorized Representative (LAR) proxy informed consent with patient’s assent
DRUG DOSAGE AND FORMULATION	
Two dosing levels of T-817MA (224 and 448 mg/day) or placebo. The 448 mg dose arm will be started at 224 mg for 4 weeks, and then increased to 448 mg.
 
Film-coated tablets are 112 mg T-817MA or placebo and dispensed in blister packs.
 
The study medication will be taken once daily after breakfast.

ROUTE OF ADMINISTRATION	Oral
TREATMENT DURATION	Duration of treatment is 52 weeks. There is also a screening period of up to 6 weeks; and a 4-week post-treatment observation period. Each patient may participate in the study for up to 62 weeks.
PROCEDURES	
Physical examinations, cognitive and functional test batteries, clinical and research venipunctures, volumetric MRIs, and lumbar puncture in a subset of patients.
 
Visits: Screening (within 42 days prior to randomization),

	Baseline (Week 0), Weeks 4, 8, 12, 18, 24, 30, 36, 44, 52, and 56 (follow-up)
--	---

STATISTICAL METHODS

1.1 Sample Size Determination

The change in the ADAS-cog score in the placebo group is expected to be 3.5 points in one year. Assuming that the difference in the ADAS-cog scale between each T-817MA treatment group and the placebo group is 2.5 points after one year, with a Standard Deviation of 6.5, the required number of cases to show a significant difference in the ADAS-cog is estimated at 110 per group. This calculation has 80% statistical power at the 5% significance level.

The power calculation of 80% as shown above corresponds to achieving significance on the ADAS-cog alone, which would be considered a successful outcome for a proof of concept study. Achieving significance on both co-primary endpoints is not fully powered, but would be considered a successful outcome for a pivotal study.

In order to have 110 evaluable patients in each group, it is necessary to randomize at least 450 patients (at least 150 per group) to double-blind treatment, assuming a 26% dropout rate during the treatment period.

1.2 Randomization and Stratification

Each patient will be randomly allocated in a 1:1:1 ratio into one of the 3 groups: treatment with 448 mg or 224 mg of T-817 or placebo. A randomization schedule will be generated and incorporated into the Electronic Data Capture system (EDC) and the treatment group will be assigned as the site activates the patient. A centralized eligibility evaluation procedure will be applied for each patient. A stratified permuted block randomization procedure will be used. Site and baseline MMSE will be stratification factors.

1.3 Protocol Deviations, Data Blind Review, and Unblinding

Classification of deviations from the protocol as minor or major, and decisions regarding exclusion of patients and/or patient data from the statistical analyses, will be decided on a case-by-case basis without knowledge of the treatment assigned and before

the database lock (Data Blind Review). After database lock, the responsible statistician will request the treatment codes, the study will be unblinded, and the statistical analysis will be conducted.

1.4 Analysis Populations

Analysis populations are defined as follows:

- The Safety population will include all randomized patients who took at least one dose of the study medication.
- The modified Intent-to-Treat (mITT) population will include all randomized patients who took at least one dose of the study medication and who have at least one efficacy evaluation following baseline.
- The Per Protocol (PP) population will include all mITT patients who:
 - took the assigned medication during the 52 weeks of treatment, and
 - did not have any major protocol deviations.

The primary population for efficacy analysis is the mITT population. Analysis of primary and secondary efficacy endpoints will be performed in the mITT and PP populations. The safety population will be used for analyses of safety endpoints.

1.5 Efficacy Endpoints

1.5.1 Primary Efficacy Endpoints

The co-primary efficacy endpoints are the change in the ADAS-cog and ADCS-CGIC from Baseline to Week 52 between each T-817MA treatment group (high dose or low dose) and the placebo group in the mITT population. A Mixed-effects Model Repeated Measure will be used to calculate the differences in change of ADAS-cog at 52 weeks, with baseline ADAS-cog score as covariate. A Mixed-effects Model Repeated Measure will be used to calculate the differences in change of ADCS-CGIC at 52 weeks.

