1.5.2 Secondary Efficacy Endpoints

1. The change in the following assessments from Baseline to Week 52 between each T-817MA treatment group (high dose and low dose) and the placebo treatment group in the mITT population:
 - a. ADCS-ADL
 - b. FAQ
 - c. NPI

d. MMSE

A Mixed-effects Model Repeated Measure will be used to calculate differences at 52 weeks, using baseline assessment as a covariate.

2. The following will also be analyzed in the mITT population:
 - a. The change in ADAS-cog, ADCS-CGIC, ADCS-ADL, FAQ, NPI and MMSE from Baseline to Weeks 12, 24 and 36
 - b. The change in ADAS-cog, ADCS-CGIC and MMSE from Baseline to Week 44
 - c. The change in ADAS-cog and MMSE from Baseline to Week 56
3. Primary and secondary endpoints will similarly be assessed in the per-protocol population.

1.6 vMRI

Observed Case analysis for differences in change of vMRI over 52 weeks with mITT and PP.

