1.9 Statistical Methods

Complete details of efficacy and safety analyses will be provided in a separate Statistical Analysis Plan (SAP).

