1.9.1 Efficacy Analysis

Analysis of primary and secondary efficacy endpoints will be performed on the mITT, and PP populations.

The primary efficacy hypothesis is that treatment with one or both of the T-817MA doses will result in a statistically significant reduction in total ADAS-cog score relative to the placebo group at Week 52 in the mITT population. The first stage in the hierarchical analysis will test the statistical hypothesis of no difference between the three treatment groups.

A hierarchical strategy will be used to preserve alpha: the primary analysis will first compare the high dose arm to placebo at an alpha level of 0.05, and if this is positive the low dose group will be compared to placebo again at an alpha level of 0.05.

The first stage in the hierarchical analysis will test the statistical hypothesis of no difference between the three treatment groups.

Categorical variables will be summarized by treatment group using frequency distribution: number of non-missing observations (N) and percentages (%). Percentages will be calculated within each treatment group on the number of non-missing observations. Continuous variables will be summarized using standard quantitative statistics: number of non-missing observations (N), mean, standard deviation (SD), median and range (minimum and maximum observed values).

OC and Imputation analysis of primary and secondary efficacy endpoints (the change in ADAS-cog and MMSE from Baseline to Weeks 12, 24, 36, 44, 52 and 56, the change in ADCS-ADL, FAQ and NPI from Baseline to Weeks 12, 24, 36 and 52 and the change in ADCS-CGIC from Baseline to Weeks 12, 24, 36, 44 and 52) will be performed in the mITT and PP populations.

Subgroup analysis (e.g. gender, age, baseline MMSE score) will be performed in the mITT and PP populations.

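### Randomisation is stratified by site and baseline MMSE, but the listed primary models include neither and the ADCS-CGIC model lists no covariate, so precision is lost if these factors are prognostic

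*Combined protocol and SAP*

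**What the plan says.** Section 1.2 (Randomization and Stratification) uses permuted blocks within strata and states: "Site and baseline MMSE will be stratification factors".

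Section 1.5.1 (Primary Efficacy Endpoints) gives the two co-primary models. The ADAS-cog MMRM is fitted "with baseline ADAS-cog score as covariate". The ADCS-CGIC sentence is "A Mixed-effects Model Repeated Measure will be used to calculate the differences in change of ADCS-CGIC at 52 weeks" and stops there.

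Section 1.5.2 (Secondary Efficacy Endpoints) fits the Week 52 models for ADCS-ADL, FAQ, NPI and MMSE "using baseline assessment as a covariate".

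No section puts site in an efficacy model. Baseline MMSE enters only where MMSE is itself the outcome. It is otherwise a subgroup variable in section 1.9.1: "Subgroup analysis (e.g. gender, age, baseline MMSE score) will be performed in the mITT and PP populations".

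Section 1.9 leaves complete analysis details to a separate SAP, which is not among the documents. Section 1.1 says of success on both endpoints: "Achieving significance on both co-primary endpoints is not fully powered".

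**The concern.** Stratified blocks force the arms to be nearly balanced on site and MMSE stratum, so differences between strata contribute little to the true variance of the treatment contrast. A model without the strata still counts those differences as residual error. When the strata are prognostic, the model-based standard error is then larger than the real one, the test rejects less often than its nominal 5% under the null, and power is lost compared with a model that includes the strata.

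The ADCS-CGIC model is the barer of the two. As listed, this co-primary has less covariate adjustment than any Week 52 secondary scale. It is also the endpoint on which the second, not fully powered definition of success depends.

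**Working it through.** **Inputs.** From section 1.1: difference 2.5 points, SD 6.5, 110 evaluable per group, 5% level (taken as two-sided), 80% power. The documents give no R² for site or MMSE, so R² is assumed. It means the share of outcome variance that these factors explain beyond the covariates already in the model, with 6.5 taken as the SD before they are added.

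**The plan's own figure.**
- n per group = 2 × (1.96 + 0.8416)² × 6.5² / 2.5² = 106.1, so 107. The plan states 110. A one-sided test would need 84, so two-sided is the reading that fits.
- At 110 per group, SE = 6.5 × √(2/110) = 0.876 and 2.5/0.876 = 2.852. Power = Φ(2.852 − 1.96) = 81.4% (81.1% by the t distribution).

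The sample size reproduces; there is no error in it.

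**Effect of omitting the strata.** Let k = √(1 − R²), with strata balanced by design.
- Reported SE / true SE = 1/k
- True size of the nominal 5% test = 2 × (1 − Φ(1.96/k))
- Unadjusted power = Φ((2.852 − 1.96)/k)
- Adjusted power = Φ(2.852/k − 1.96)
- Adjusted 95% half-width = 1.96 × 0.876 × k
- Equivalent extra patients per arm = 110 × ((1 + 1.96 × (1 − k)/2.852)² − 1)

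The unadjusted power formula credits the unadjusted test with the balance that stratification provides, so the comparison does not exaggerate the gain.

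| Assumed R² | SE too large by | True size | Power, unadjusted | Power, adjusted | Gain (points) | Half-width, adjusted | Extra patients per arm |
|---|---|---|---|---|---|---|---|
| 0% | 0% | 5.0% | 81.4% | 81.4% | 0 | 1.72 | 0 |
| 2% | 1.0% | 4.8% | 81.6% | 82.2% | 0.5 | 1.70 | 1.5 |
| 5% | 2.6% | 4.4% | 82.0% | 83.3% | 1.3 | 1.67 | 3.9 |
| 10% | 5.4% | 3.9% | 82.7% | 85.2% | 2.6 | 1.63 | 7.9 |
| 15% | 8.5% | 3.4% | 83.4% | 87.2% | 3.8 | 1.58 | 12.1 |

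Gains are taken before rounding. The unadjusted half-width is 1.72 ADAS-cog points throughout. Starting from exactly 80% power instead (2.8016 in place of 2.852), the gains are 0 / 0.6 / 1.4 / 2.7 / 4.0 points.

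**Simulation check.** The assumptions were: Week 52 only, three arms of about 110, blocks of 3 within site by two MMSE strata, and uneven site sizes. There were 3,000 to 4,000 runs for power (Monte Carlo error about 0.6 to 0.7 points) and 5,000 for size. Site counts are assumed because the documents give none.

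| Model | Power, 50 sites, MMSE and site each 5% of variance | Power, nothing prognostic, 30 sites / 50 sites |
|---|---|---|
| Unadjusted | 81.8% | 81.1% |
| MMSE | 83.7% | 81.2% |
| MMSE + fixed site | 83.2% | 79.9% / 79.2% |
| MMSE + random site | 85.1% | 81.5% / 81.4% |

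In the prognostic scenario, size was 3.9% unadjusted and 4.9% with MMSE plus random site. This agrees with the 10% row of the closed form. It also shows that fixed site terms cost power when site is not prognostic, whereas random site does not.

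**ADCS-CGIC.** Section 1.1 gives no effect size or SD for this endpoint, so no power can be computed.

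**The case against.** The strongest reply is that this is a synopsis. Section 1.5.1 also leaves out visit, treatment-by-visit and the covariance structure, which any MMRM needs, and section 1.9 sends the detail to another document. Silence about site and MMSE is therefore weak evidence about the final model. That stands: the finding is that the terms are not listed here, not that the analysis omitted them. But 1.5.1 does name a covariate for one model, and what it names does not match the randomisation.

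Second, the harm is small and in the safe direction. Baseline ADAS-cog probably captures part of what MMSE would explain, so the extra R² for ADAS-cog may be near the bottom of the range: 2 to 5% gives 0.5 to 1.3 points. The mITT MMRM may also carry more information than 110 completers. At an assumed effective 130 per arm, power is already 87.3% and the gain at R² of 5% and 10% falls to 1.0 and 1.9 points. This stands and limits the size of the point. It does not cover site, or ADCS-CGIC, where no severity covariate is listed.

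Third, the size figures apply only to variance balanced by randomisation. Leaving baseline ADAS-cog, or the within-stratum part of continuous MMSE, out of the ADCS-CGIC model loses precision but keeps size nominal. The closed form also assumes near-perfect balance, which 26% dropout can erode. Both are right. A further simulation with 26% random dropout still showed the same direction, with no loss from adding MMSE when it was not prognostic.

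Last, no section describes a baseline ADCS-CGIC score, so the contrast with the secondary scales cannot mean that its own baseline was forgotten. This is fair, and it is why another scale's baseline is proposed.

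**Conclusion.** The concern holds. The listed primary models omit both stratification factors, and the ADCS-CGIC model lists no covariate. If site or baseline MMSE is prognostic beyond the terms already present, the analysis as written is conservative and less precise than the design allows. For ADAS-cog the cost is 0 to 3.8 points of power over an assumed residual R² of 0 to 15%; if R² is zero there is none. It is neither a bias, nor an inflation of type I error, nor a shortfall against the 80% stated for ADAS-cog. The larger loss may be on ADCS-CGIC, but its size is unknown. The change is worth making, with medium confidence, because R² is assumed and the separate SAP may already contain the terms.

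**What to change.** In section 1.5.1:
- Add baseline MMSE (stratum or continuous) to both primary MMRMs.
- Add baseline ADAS-cog to the ADCS-CGIC MMRM as a baseline severity covariate.
- Include site as a random effect, or with small sites pooled by a rule fixed before unblinding. Do not enter many separate fixed site terms.

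In section 1.5.2, add baseline MMSE to the secondary MMRMs, except the MMSE endpoint, which already has it.

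If the separate SAP already specifies these terms, repeat them in 1.5.1 so that the two documents agree.

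The cost is drafting: the variables are already collected, and sample size and alpha are unchanged. The one real decision is the random-effect or pooling rule for site, which must be written down before the treatment codes are released.

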1.5.2 Secondary Efficacy Endpoints

1. The change in the following assessments from Baseline to Week 52 between each T-817MA treatment group (high dose and low dose) and the placebo treatment group in the mITT population:
 - a. ADCS-ADL
 - b. FAQ
 - c. NPI

d. MMSE

A Mixed-effects Model Repeated Measure will be used to calculate differences at 52 weeks, using baseline assessment as a covariate.

2. The following will also be analyzed in the mITT population:
 - a. The change in ADAS-cog, ADCS-CGIC, ADCS-ADL, FAQ, NPI and MMSE from Baseline to Weeks 12, 24 and 36
 - b. The change in ADAS-cog, ADCS-CGIC and MMSE from Baseline to Week 44
 - c. The change in ADAS-cog and MMSE from Baseline to Week 56
3. Primary and secondary endpoints will similarly be assessed in the per-protocol population.

1.6 vMRI

Observed Case analysis for differences in change of vMRI over 52 weeks with mITT and PP.

1.7 CSF Substudy

Observed Case analysis for differences in change of CSF biomarkers over 52 weeks with mITT and PP.

1.8 Safety Endpoints

- Occurrence of adverse events (AEs)
- Clinical laboratory tests
- Vital signs
- Physical examinations
- ECGs
- Use of concomitant medications
- C-SSRS Pediatric

1.9 Statistical Methods

Complete details of efficacy and safety analyses will be provided in a separate Statistical Analysis Plan (SAP).

1.9.1 Efficacy Analysis

Analysis of primary and secondary efficacy endpoints will be performed on the mITT, and PP populations.

The primary efficacy hypothesis is that treatment with one or both of the T-817MA doses will result in a statistically significant reduction in total ADAS-cog score relative to the placebo group at Week 52 in the mITT population. The first stage in the hierarchical analysis will test the statistical hypothesis of no difference between the three treatment groups.

A hierarchical strategy will be used to preserve alpha: the primary analysis will first compare the high dose arm to placebo at an alpha level of 0.05, and if this is positive the low dose group will be compared to placebo again at an alpha level of 0.05.

The first stage in the hierarchical analysis will test the statistical hypothesis of no difference between the three treatment groups.

Categorical variables will be summarized by treatment group using frequency distribution: number of non-missing observations (N) and percentages (%). Percentages will be calculated within each treatment group on the number of non-missing observations. Continuous variables will be summarized using standard quantitative statistics: number of non-missing observations (N), mean, standard deviation (SD), median and range (minimum and maximum observed values).

OC and Imputation analysis of primary and secondary efficacy endpoints (the change in ADAS-cog and MMSE from Baseline to Weeks 12, 24, 36, 44, 52 and 56, the change in ADCS-ADL, FAQ and NPI from Baseline to Weeks 12, 24, 36 and 52 and the change in ADCS-CGIC from Baseline to Weeks 12, 24, 36, 44 and 52) will be performed in the mITT and PP populations.

Subgroup analysis (e.g. gender, age, baseline MMSE score) will be performed in the mITT and PP populations.

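### The 80% power in section 1.1 reaches only the high dose: under the high-dose-first rule of section 1.9.1 the low dose has about 70%, and a low-dose-only result cannot be declared

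*Combined protocol and SAP*

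**What the plan says.** Three statements in the combined protocol and SAP bear on this point.

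- **Hypothesis (section 1.9.1).** The primary efficacy hypothesis, at Week 52 in the mITT population, is that "one or both of the T-817MA doses will result in a statistically significant reduction in total ADAS-cog score relative to the placebo group".
- **Decision rule (section 1.9.1).** To protect alpha, 448 mg is tested against placebo first, at the 0.05 level. The second step is conditional on that result: "if this is positive the low dose group will be compared to placebo again at an alpha level of 0.05". The same section also says, twice, that a three-group test of no difference is the first stage. It does not say whether that test gates the dose comparisons, or at what level.
- **Power (section 1.1).** The calculation rests on this assumption: "the difference in the ADAS-cog scale between each T-817MA treatment group and the placebo group is 2.5 points after one year". It takes an SD of 6.5 and arrives at 110 per group. It then says: "This calculation has 80% statistical power at the 5% significance level". The section adds that this power is for ADAS-cog alone.

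Section 1.1 makes no allowance for the ordered testing and gives no separate power for the low dose.

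**The concern.** The power statement and the decision rule describe different procedures. Section 1.1 assumes the same effect in each dose group and reports one power figure, so a reader will naturally apply 80% to both doses. Under the rule in section 1.9.1 the two doses are not treated alike. The high dose needs one significant comparison, while the low dose needs two.

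The hypothesis has a related gap. Success on either dose or on both covers three outcomes: high only, both, and low only. The rule can return the first two but never the third. The plan neither says so nor says how a nominally significant 224 mg result would be reported after 448 mg misses.

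At stake is what the trial can say about dose. Someone relying on section 1.1 would overestimate the chance of a confirmatory claim for 224 mg. Without a reporting rule, a low-dose result after a failed high-dose test could be presented as if it met the stated hypothesis.

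**Working it through.** **Inputs.** From section 1.1: difference 2.5 points for each dose against placebo, SD 6.5, 110 evaluable per group, 80% power, 5% level, 26% dropout. From section 1.2: 1:1:1 allocation, hence one placebo arm shared by both comparisons. Sidedness is not stated.

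**Step 1. Reproduce the plan's sample size.**

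n per group = 2 × (z_α + z_β)² × SD² / difference²

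- Two-sided 5%: 2 × (1.960 + 0.842)² × 6.5² / 2.5² = 106.1, so 107 per group, close to the stated 110.
- One-sided 5%: 2 × (1.645 + 0.842)² × 6.5² / 2.5² = 83.6, so 84 per group, which does not match.

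The two-sided reading is therefore used below. The dropout figure also agrees: 110 / 0.74 = 148.6, so 149, against the stated 150.

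**Step 2. Power of one pairwise comparison at 110 per group.**

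- Standard error = 6.5 × √(2/110) = 0.876.
- Standardised effect = 2.5 / 0.876 = 2.852.
- Power = Φ(2.852 − 1.960) = Φ(0.892) = 81.4% (81.1% by the noncentral t).

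This reproduces the plan's 80%. It is the high-dose power when 448 mg is tested first.

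**Step 3. Power to declare the low dose under the sequence.** The low dose is declared only if both comparisons are significant in favour of T-817MA. With equal arms and a shared placebo, the two test statistics have correlation 0.5. The required probability is

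Φ₂(0.892, 0.892; ρ = 0.5) = 70.6%,

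where Φ₂ is the bivariate normal distribution function. A simulation of one million trials, with three arms and pooled variance, gave 70.4%.

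**Step 4. Sensitivity to readings that the plan leaves open.**

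| Setting | High dose | Low dose under the sequence |
|---|---|---|
| 107 per group | 80.3% | 69.2% |
| 110 per group (plan) | 81.4% | 70.6% |
| 111 per group (150 × 0.74) | 81.7% | 71.1% |
| 110, three-group test also gates at an assumed 0.05 (simulation) | 77.1% | 69.8% |

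The low-dose figure stays near 70% in every row.

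**Step 5. Outcomes the rule can return.**

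| Result of the two comparisons | Covered by the hypothesis | Can be declared |
|---|---|---|
| 448 mg only | Yes | Yes |
| Both doses | Yes | Yes |
| 224 mg only | Yes | No |

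**The case against.** The strongest reply is that nothing here is an error. Testing the high dose first is a standard way to control alpha, and giving up a low-only claim is its known price. The hypothesis and the rule stand in the same section, so a careful reader can see that low-only is not confirmatory. Quoting pairwise power is common. Sections 1.5.1 and 1.5.2 still provide an estimate for each dose against placebo, so the low-dose data would not be lost. The primary analysis is a repeated-measures model in the mITT population with at least 150 randomized per group, so dropouts with post-baseline data also contribute. If all 150 contributed in full, the same calculation would give about 86% for the low dose. Finally, section 1.9 defers complete details to a separate SAP.

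Much of this stands. The order of testing needs no change. The 86% is an upper bound, not a forecast, and section 1.1 itself bases power on 110 evaluable patients, but it does show that the 70% must carry its conditions. A separate SAP would not correct the power and hypothesis statements made here.

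Four stronger readings are tempting, and the documents do not support them:

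- *That the plan claims 80% for the low dose under the hierarchy.* It does not say so. In section 1.1, the word each attaches to the assumed difference, and the 80% belongs to the pairwise calculation. The fault is a figure left unqualified.
- *That the hypothesis is flatly contradicted.* High-only and both remain reachable. Only low-only is excluded.
- *That the low dose almost never succeeds.* This requires a high-dose effect well below the 2.5 points that section 1.1 assumes, and nothing in the plan supplies such a value.
- *That a positive result means significance on both co-primary endpoints, which would lower the figures further.* Section 1.9.1 states the hypothesis on ADAS-cog, and section 1.1 accepts ADAS-cog alone as proof-of-concept success. The plan gives no ADCS-CGIC power or correlation from which to compute anything else.

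**Conclusion.** The point holds as a mismatch between the stated power, the stated hypothesis and the decision rule. On the plan's own figures, the 80% applies to 448 mg (81.4% when recomputed). The power to declare 224 mg is 70.6%, lower by 81.4 − 70.6 = 10.8 percentage points. A success confined to 224 mg falls within the hypothesis but cannot be declared.

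The 70% rests on a true effect of 2.5 points for both doses, SD 6.5, 110 evaluable patients per arm, a shared placebo arm, two-sided 5% tests (assumed) and ADAS-cog alone. It hardly changes if the three-group test also gates at an assumed 0.05. A reader might infer inflated type I error or an invalid design; neither follows, because the sequence controls alpha across the two dose comparisons.

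**What to change.** Keep the sequence and the sample size, and change the wording in two places.

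- **Section 1.1.** State that the 80% applies to the comparison of 448 mg with placebo. Add that, under the high-dose-first sequence, power to declare 224 mg is about 70%, assuming 2.5 points on both doses, SD 6.5, 110 evaluable per group, a shared placebo arm and two-sided 5% tests. State the sidedness.
- **Section 1.9.1.** Restate the hypothesis in the order tested: 448 mg is superior to placebo on ADAS-cog at Week 52 and, only if that is shown, 224 mg is superior to placebo. Add that a nominally significant 224 mg result after a failed 448 mg test is exploratory.

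This needs no extra patients and no change to the analysis. The cost is that the stated low-dose power becomes less favourable. For scale, keeping the sequence and giving the low dose 80% would take about 133 evaluable per group, or 133 / 0.74 = 179.7, so 180 randomized per group. The point does not ask for that increase.
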